In addition, the model for hemodynamic predictors of postoperative mortality developed from machine learning will perform better in terms of discrimination (C-statistics), calibration (Hosmer-Lemeshow test), and risk reclassification (Yates slope and integrated discrimination improvement) than the Surgical Apgar Score.

Methodology

Study Design Overview

This is a retrospective population cohort study. Following approval from the Research Ethics Board, we will analyze de-identified records of our study population. Since there are many machine modelling techniques each with its benefits and drawbacks, we will create models using interpretable machine learning techniques we believe will work the best for this study, and test the performances of these models through internal validation. The models will be compared to the Surgical Apgar Score in terms of discrimination, calibration, and risk reclassification. The trial will be registered on ClinicalTrials.gov prior to receiving research data and performing analysis. Transparent reporting of a multivariable prediction model for individual prognosis or diagnosis (TRIPOD) and Developing and Reporting Machine Learning Predictive Models (24) guidelines will be followed.

Study Population

We will include all patients ages ≥ 45 receiving their index (i.e. first) non-cardiac surgery with an overnight stay at the Nova Scotia Health Authority Queen Elizabeth II (QEII) hospitals (Victoria General and Halifax Infirmary) Halifax, Canada, from the past five years (i.e. January 1, 2013 to December 1, 2017). For patients who had multiple surgeries, only the first non-cardiac surgery with an overnight stay at QEII will be included to avoid confounding from previous surgical admissions (i.e. one surgical admission per patient). We chose December 1, 2017, as the end date to allow for complete data 30 days after surgery: for data analysis in summer 2019, we only have access to mortality data up to December 31, 2017.

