We will exclude patients with no intraoperative anesthetic records. Cardiac surgery patients (identified by procedure anatomy “Heart” or “Cardiac” within Innovian) are excluded since they have a unique set of considerations and complications due to having surgery directly in the heart. To include the full spectrum of non-cardiac surgical patients, no specific surgeries will be excluded except for deceased organ donation (“organ retrieval” in Innovian procedure name, and American Society of Anesthesiologists classification for neurologically-deceased organ donors, ASA=VI).

Preliminary analysis of our intraoperative database estimates approximately 35,000 patients in this cohort. For patients with multiple procedures, the date of the first surgical procedure with an overnight stay will be used to identify the specific surgical admission of interest.

Data Sources

The de-identified dataset will consist of databases from Innovian, Horizon Surgical Manager (HSM), and Health Data Nova Scotia (HDNS). Innovian is the intraoperative anesthesia electronic information management system used at the QEII, containing automated recordings of intraoperative standard monitors, time-stamped anesthesiology entries of medications and interventions, and perioperative laboratory tests. HSM contains vital signs and administrative data at the anesthetic preoperative clinic, in the preoperative area prior to the surgery, and in the recovery room after surgery.

The specific HDNS databases to which access is being requested are the Canadian Institute for Health Information (CIHI) Discharge Abstract Database (DAD) and Vital Statistics. DAD is a repository of clinical and administrative data from each hospitalization, including preoperative diagnoses, surgery performed, postoperative complications, and investigations.

DAD includes the 25 most relevant diagnoses preoperatively and postoperatively. Nova Scotia physician billings data will not provide any additional relevant information and are not necessary for this project. The Vital Statistics database records all deaths within Nova Scotia. Innovian and HSM data will be linked together by health card number and surgical date by the Innovian Data Manager (Innovian-HSM dataset). The health card numbers will be sent to Medavie for encryption. HDNS will link the Innovian-HSM dataset with the HDNS variables by encrypted study IDs and surgery date. National and provincial privacy and data security policies will be strictly followed.

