Data linkage:

Step 1: Innovian

- a. Include patients with surgery dates 2013 Jan 1 – 2017 Dec 1 inclusive
- b. Include patients with age on date of surgery ≥ 45
- c. Exclude patients with procedure name that includes “organ retrieval” or ASA = VI, as well as procedure anatomy “heart” or “cardiac”.
- d. Eligible patients will be linked to HSM by health card number for the required variables described in the Appendix.

Step 2: HDNS: CIHI DAD

- a. Health card numbers of patients identified in Step 1 will be sent to Medavie for encryption. Medavie will provide HDNS with encrypted health card numbers. HDNS obtains Study ID and Surgery date from the Innovian-HSM dataset to perform linkage via Study ID, encrypted health card number and procedure date (to ensure the data is from the same surgical admission). The maximum allowable mismatch for the surgery dates in Innovian and CIHI is $+$ / $- 1$ day. The Innovian surgery date will be used as the gold standard, since the record is done in real time and thus the most accurate.
- b. Exclude patients with Length of Stay (LOS) ≤ 1 . If a patient had multiple surgeries, the first surgery with a LOS >1 (i.e. at least overnight stay) will be included.
- c. HDNS provides Innovian-HSM the final list of included patients (patient ID and surgery date). Innovian-HSM will then send data for relevant variables to HDNS for linkage.

Data quality: Data reabstraction studies performed by the CIHI show high data quality, ranging from 76 to 96% for coding consistency of interventions reported, significant diagnoses, and most responsible diagnosis (25). Since intraoperative hemodynamic variables and laboratory are automatically recorded into Innovian, no validation is necessary. It would not be possible to retrospectively validate the anesthesiology physician entries into Innovian (e.g. use of vasopressor medications) as most are not recorded elsewhere, but with medical-legal requirements and more than 10 years of experience with Innovian at QEII, the error rates will likely not significantly affect results.

Variables

Please see Appendix for a detailed table of all variables.

I. Main Predictors (“Exposures”)

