Appendix 1. Summary of Variables

Source Dataset	Variable	Level of Identification	Time Span	Why is this element required in the analysis?
Information for inclusion and data linkage				
Innovian	Date of surgery	Patient	Jan 1, 2013 to Dec 1, 2017	
Part of HDNS data linkage with Innovian to ensure only variables from the surgical admission of interest (first surgery admission with LOS>1) is included. This Date of Surgery will be used to confirm linkage with “PDATE” from CIHI DAD to ensure that data from the correct surgical admission is included. The maximum allowable mismatch for the surgery dates in Innovian and CIHI is +/- 1 day. The Innovian surgery date will be used as the gold standard, since the record is done in real time and thus the most accurate.
 
The date of surgery will also be used to divide the cohort temporally into the derivation/training group (January 1, 2013 – November 30, 2016), and validation group (December 1, 2016 – December 1, 2017)

Innovian	Patient_ID: encrypted health card number	Patient	Jan 1, 2013 to Dec 1, 2017	HDNS data linkage with Innovian. The dataset given to us will not contain Patient_ID, but rather a Study ID.
Innovian	Age: on date of surgery	Patient	Jan 1, 2013 to Dec 1, 2017	Age ≥ 45 part of inclusion criteria. Also, as age may impact outcomes, this will be included as a covariate in our models
Innovian	Organ donation: Procedure name	Patient	Jan 1, 2013 to Dec 1, 2017	Patients with procedure name that includes “organ donor” or “organ donation” will be excluded, since they are already declared brain dead and

	containing the word “Organ donor” or “Organ donation” or “DCD” [Derived by Innovian]			will not reflect the usual surgical population.
Innovian	Cardiac surgery [Derived by Innovian]	Patient	Jan 1, 2013 to Dec 1, 2017	As defined by ProcedureAnatomy = “heart” or “cardiac”. Cardiac surgery patients are excluded since they are receiving surgery directly on the heart and have a unique set of complications that may not reflect the usual surgical population.
Innovian	ASA: American Society of Anesthesiologist class (I to VI)	Patient	Jan 1, 2013 to Dec 1, 2017	Patients with ASA VI (i.e. patient with neurologic brain death for organ donation) will be excluded. Also, as this may affect outcomes, it will be included as a covariate in our models.

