CIHI DAD	PCODE[1-n]: Procedure [1-n] Code, according to Classification of Health Interventions (CCI). The one PCODE corresponding to the specific PDATE will be obtained, i.e. the corresponding number (e.g. PDATE1) will be used for all procedure-related codes (i.e. PCODE1)	Patient	Jan 1, 2013 to Dec 1, 2017	Covariate in model The PCODE corresponding to the included PDATE for each patient will be included for modeling as a covariate.
CIHI DAD	PDSERV[1-n]: Procedure [1-n] Doctor service The one PDSERV corresponding to the specific PDATE will	Patient	Jan 1, 2013 to Dec 1, 2017	The one PDSERV corresponding to the included PDATE allows us to determine the surgical service, and since the type of surgery may affect outcomes, it will be included as a covariate. We will include the following PDSERV: 00030 General Surgery 00031 Cardiac Surgery 00032 Neurosurgery 00034 Orthopedic Surgery 00035 Plastic Surgery

	be obtained, i.e. the corresponding number (e.g. PDATE1) will be used for all procedure-related codes (e.g. PDSERV1)			00036 Thoracic Surgery 00037 Vascular Surgery 00039 Urology 00050 Obstetrics and Gynecology 00059 Colorectal Surgery 00060 Otolaryngology 00073 General Surgical Oncology
Intraoperative variables				
Innovian	SBP: Systolic blood pressure [Derived by Innovian as multiple variables – see right]	Patient	Jan 1, 2013 to Dec 1, 2017	Exposure variable to be included into modeling. The following variables will be derived by Innovian: 5. Maximum change from preoperative SBP, in a) absolute change (mmHg), and b) relative change (%) (emergency and elective cases analyzed separately due to the lack of preoperative blood pressure in the emergency group) 6. Cumulative duration (minutes) $\geq 20\%$ below preoperative SBP 7. Longest single episode (minutes) below a) 80, b) 90, and c) 100 mmHg 8. Cumulative duration (minutes) below a) 80, b) 90, and c) 100 mmHg
Innovian	MAP: Mean Arterial Pressure	Patient	Jan 1, 2013 to Dec 1, 2017	Exposure variable to be included into modeling. The following variables will be derived by Innovian: 1. Maximum change from preoperative MAP, in a) absolute change (mmHg), and

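### The plan does not settle whether the cardiac and organ-retrieval exclusions remove patients or surgery records, and either reading admits or drops the wrong index cases

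*Combined protocol and SAP*

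**What the plan says.** All places are in the combined protocol and SAP.

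- **Data linkage, Step 1, item c:** "Exclude patients with procedure name that includes “organ retrieval” or ASA = VI, as well as procedure anatomy “heart” or “cardiac". This comes before any index operation has been selected.
- **Data linkage, Step 2, item b:** the index is chosen afterwards. "If a patient had multiple surgeries, the first surgery with a LOS >1 (i.e. at least overnight stay) will be included".
- **Study Population, cohort definition:** "For patients who had multiple surgeries, only the first non-cardiac surgery with an overnight stay at QEII will be included". This describes operations being passed over, not people being removed.
- **Study Population, exclusions:** "Cardiac surgery patients (identified by procedure anatomy “Heart” or “Cardiac” within Innovian) are excluded". The reason given is that surgery on the heart itself brings its own considerations and complications.
- **Appendix 1, cardiac surgery row:** the same Innovian field is used. "As defined by ProcedureAnatomy = “heart” or “cardiac".
- **Appendix 1, PDSERV row:** the list of surgical services to be included contains "00031 Cardiac Surgery", without comment.

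No section states whether Step 1c acts on the person or on the single surgery record. None says what happens when a cardiac operation comes before a non-cardiac one in the same stay.

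**The concern.** Two programmers could code Step 1c differently, and each version has a fault.

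If the rule removes people, eligibility can depend on what happens after the index operation. Someone who has an eligible craniotomy, dies neurologically and has a retrieval record days later would vanish from the cohort, although this is a primary-outcome death. Someone with bowel surgery in 2013 and heart surgery in 2016 would also vanish, and that person must have survived to reach the second operation.

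If the rule removes records, those cases stay. But a laparotomy shortly after heart surgery in the same admission can become the index non-cardiac case. Its risk of death then reflects the cardiac operation, which the plan set out to keep away from this cohort.

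The choice may be hard to revisit. The ethics section says that only information from the first surgery is collected, and Appendix 1 requests only the one procedure code and one service code that match the index date. Analysts working on the delivered dataset would not see the other operations, so the rule needs settling at linkage.

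**Working it through.** **1. Which unit does the wording support?**

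- For the person: Step 1c and the Study Population exclusion both speak of patients. Step 2a sends forward the health card numbers of patients identified in Step 1.
- For the record: Steps 1a and 1b also speak of patients while testing attributes of an operation (its date, and age on that date). Step 2b speaks of excluding patients by length of stay, yet keeps someone with several operations through the first one that qualifies. Step 2c returns pairs of patient and surgery date. The cohort definition takes the first non-cardiac operation.

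The record reading has more support, but the text does not close the question.

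**2. Both readings applied to five constructed patients**

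| Patient | Sequence | Person-level rule | Record-level rule | Record-level plus same-admission check |
|---|---|---|---|---|
| A | hip day 0, cardiac day 400 | removed | hip | hip |
| B | craniotomy day 0, organ retrieval day 3 | removed (a 30-day death) | craniotomy | craniotomy |
| C | cardiac day 0, bowel day 300 (new admission) | removed | bowel | bowel |
| D | hip only | hip | hip | hip |
| E | cardiac, then laparotomy in the same admission | removed | laparotomy | removed |

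The person-level rule keeps one of five. The record-level rule keeps all five, including E. The combined rule keeps A to D.

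**3. Unequal exposure on the person-level reading.** Surgery dates run from January 1, 2013 to December 1, 2017. An index in January 2013 leaves almost five years in which a later cardiac record could remove it. An index in January 2017 leaves at most 11 months. The earlier (derivation) and later (validation) groups would be filtered to different degrees.

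**4. Size**

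The plan's own figure (Power calculation) reproduces: 24,000 × 0.017 = 408 deaths in the derivation group. For the whole cohort of about 35,000 the same rate gives 35,000 × 0.017 = 595.

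The remaining inputs are assumptions, because the documents give no counts:

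- *Donors with an earlier eligible operation, 1 to 25 in the window:* 1/595 = 0.17% to 25/595 = 4.2% of deaths lost. The mortality rate moves from 1.70% to between 594/34,999 = 1.70% and 570/34,975 = 1.63%.
- *Another cardiac operation in 0.1% to 3% of patients:* 35,000 × 0.001 = 35 to 35,000 × 0.03 = 1,050 patients lost. If all were alive at 30 days, the rate becomes 595/34,965 = 1.70% to 595/33,950 = 1.75%.
- *Record-level reading, 50 to 200 non-cardiac operations soon after heart surgery, with 15% to 30% mortality:* 50 × 0.15 = 7.5 to 200 × 0.30 = 60 deaths. Against 595 this is 1.3% to 10.1%. The top value needs both upper assumptions at once.

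**The case against.** The strongest reply is that the plan already means surgery records. Its linkage steps use the word patients loosely throughout, its working unit is a patient and surgery date, and its cohort definition names the first non-cardiac operation. On that reading the donor and the 2013 bowel patient both stay in. This largely stands. A reader might infer that the plan selects on future events, but that follows only from the literal wording, and nowhere does the text say that a later operation removes an earlier index.

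The reply continues that a non-cardiac operation after heart surgery in the same stay breaks no stated aim. The plan restricts to the first operation "only the first non-cardiac surgery with an overnight stay at QEII will be included to avoid confounding from previous surgical admissions", and an earlier operation in the same admission is not a previous admission. Candidate covariates such as ASA class and preoperative ICU admission would also absorb part of the risk. The point about that sentence is fair. It does not answer the separate reason in Study Population for leaving out cardiac surgery patients, which applies to someone days out from heart surgery.

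Two further inferences are tempting and unsupported. One is that Appendix 1 distrusts the anatomy label. Its cardiac surgery row adopts the same field without reservation, and its remark about entries taken from operating-room booking concerns procedure names, in the laparoscopy rows. The other is that the Cardiac Surgery service code proves mislabelled heart operations are in the cohort. The plan defines cardiac surgery by anatomy, and a cardiac service may perform an operation that is not on the heart. The entry is unexplained, and no more than that.

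**Conclusion.** The concern holds as an inconsistency in the unit of exclusion, with a real consequence on either reading. The person-level rule would drop valid index cases, some of them primary-outcome deaths, because of later operations. The record-level rule, which the text supports better, has no safeguard against an index operation that follows heart surgery in the same admission.

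The effect on the results cannot be sized from the documents. Only the 35,000 patients and the 1.7% rate are documented, and that rate is provincial in-hospital mortality after major surgery, which the plan uses as a stand-in for its primary outcome. Every other count in the ranges above is assumed. The effect is probably small overall. The point still merits correction before extraction, because it changes who is in the cohort and may not be recoverable from the delivered data.

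**What to change.** In Data linkage and Study Population, with matching text in Appendix 1:

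1. State that Step 1c applies to surgery records.
2. Choose the index as the first eligible record with the required stay.
3. State that a later cardiac or organ-retrieval record never removes an index case.
4. Exclude an index that is preceded by a cardiac-surgery record in the same admission or on the same date. Say whether such a patient leaves the cohort or moves to the next eligible operation.
5. Explain why Cardiac Surgery (PDSERV 00031) is on the included-service list. Use the code to flag cases for checking, not as an automatic exclusion, since that would also discard operations of the cardiac service that were not on the heart.

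The cost is a few sentences and one extra linkage condition. Innovian already holds the anatomy label and surgery date, and admission and discharge dates and PDSERV are already in the data request. A few post-cardiac cases are lost. The number removed under item 4 and the number flagged under item 5 should be reported, which would also supply the size that the documents cannot.

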CIHI DAD	PATIENT_ID: encrypted health card number For HDNS internal use	Patient	Jan 1, 2013 to Dec 1, 2017	HDNS data linkage with Innovian-HSM. The dataset given to us will not contain Patient_ID, but rather a Study ID.
Vital Statistics	PATIENT_ID: encrypted health card number For HDNS internal use	Patient	Jan 1, 2013 to Dec 1, 2017	HDNS data linkage with Vital Statistics. The dataset given to us will not contain Patient_ID, but rather a Study ID.
CIHI DAD	PDATE[1-n]: procedure date	Patient	Jan 1, 2013 to Dec 1, 2017	HDNS data linkage with Innovian surgery date, to ensure that only the admission corresponding to the surgery admission of interest (first surgery admission with LOS>1) is included.

				
The PDATE matching the date of procedure (+/- 1 day) from Innovian will be used. The corresponding number (e.g. PDATE1) will be used for all procedure-related codes (e.g. PCODE1, PDSERV1).
 
Note that except for preoperative comorbidity data, where we would need data for 3 years prior to PDATE, for all other variables we only need data within 30 days after PDATE.

CIHI DAD	
LOS: Length of Stay (after surgery)
 
Derived by HDNS: discharge date minus PDATE + 1 (includes day of surgery)
	Patient	
Jan 1, 2013 to Dec 1, 2018 (to account for prolonged LOS postop from the end of inclusion date)
	
Part of inclusion criteria: if a patient had multiple surgeries, the first surgery with a LOS >1 (i.e. at least overnight stay). To calculate ratio of LOS to Expected Length of Stay (ELOS) as secondary outcome. We have chosen to standardize LOS to only include duration of stay after surgery, since there are many factors that may prolong a patient's stay prior to surgery.

Additional Demographic Information				
CIHI DAD	SEX: Patient sex	Patient	
Jan 1, 2013 to Dec 1, 2017
	
As sex may affect outcomes, this will be included as a covariate in our models
 
M = Male
 
F = Female

HSM	BMI: Body Mass Index [Derived by Innovian]	Patient	
Jan 1, 2010 to Dec 1, 2017
	
Dichotomized according to WHO definition for obesity: BMI>30. This will be combined with ICD code to create a binary Obesity variable (please see below).

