Innovian	Surgical APGAR Score [Derived by Innovian based on variables already requested]	Patient	Jan 1, 2013 to Dec 1, 2017	
  
 	0 points	1 point	2 points	3 points	
   
 Estimated blood loss (mL)	> 1,000	601–1,000	101–600	≤ 100	
 
 Lowest mean arterial pressure (mmHg)	< 40	40–54	55–69	≥ 70	
 
 Lowest heart rate (beats/min)	> 85	76–85	66–75	56–65	
 
 Surgical score (0-10) = sum of all points	
 
 The Surgical APGAR Score is an existing, validated method of risk stratification at the end of surgery, and will be compared to the machine learning models.	
  
		0 points	1 point	2 points	3 points	Estimated blood loss (mL)	> 1,000	601–1,000	101–600	≤ 100	Lowest mean arterial pressure (mmHg)	< 40	40–54	55–69	≥ 70	Lowest heart rate (beats/min)	> 85	76–85	66–75	56–65	Surgical score (0-10) = sum of all points					The Surgical APGAR Score is an existing, validated method of risk stratification at the end of surgery, and will be compared to the machine learning models.					4 points
	0 points	1 point	2 points	3 points																															
Estimated blood loss (mL)	> 1,000	601–1,000	101–600	≤ 100																															
Lowest mean arterial pressure (mmHg)	< 40	40–54	55–69	≥ 70																															
Lowest heart rate (beats/min)	> 85	76–85	66–75	56–65																															
Surgical score (0-10) = sum of all points																																			
The Surgical APGAR Score is an existing, validated method of risk stratification at the end of surgery, and will be compared to the machine learning models.																																			
Mortality																																			
Vital Statistics	Mortality (30-day all cause) [Derived by HDNS based on DOD from Vital Statistics]	Patient	Jan 1, 2013 to Dec 31, 2017	Binary outcome (yes/no), derived from DOD within 30 days from PDATE. This is needed to compute 30-day all-cause mortality. Primary outcome for the study to be used for modeling.																															

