CIHI DAD	OPDEATH: operative death	Patient	Jan 1, 2013 to Dec 31, 2017	OPDEATH will be described in descriptive statistics. 1 = Died in Operating Room 2 = Did Not Die in Operating Room																															
Vital Statistics	DOD: Date of death	Patient	Jan 1, 2013 to Dec 31, 2017	For internal use by HDNS to compute 30-day all-cause mortality (primary outcome), and the Number of																															

				postoperative day of death (i.e. Date of death minus PDATE).
CIHI DAD	Number of postoperative day of death [Derived by HDNS based on DOD from Vital Statistics]	Patient	Jan 1, 2013 to Dec 31, 2017	Derived discrete (n = 1, 2, 3... 30) variable, of the patients with 30-day mortality = yes. This variable is defined as DOD [if \leq 30 days after PDATE] minus PDATE. Survival statistics will be performed (% vs. postoperative day)
CIHI DAD	In-hospital death [Derived by HDNS based on “DISCHARGE: Discharge disposition”]	Patients	Jan 1, 2013 to Dec 31, 2017	Derived binary variable (yes/no). Of those who died within 30 days after surgery, descriptive statistics will be performed for in-hospital vs. out-of-hospital mortality (yes/no) “Yes” if DISCHARGE = 7 or 8: 7 = Died 8 = Cadaver donor admitted for organ/tissue retrieval Else = “no”
Vital Statistics	UCAUSE: Underlying Cause of Death	Patient who died within 30 days after surgery	Jan 1, 2013 to Dec 31, 2017	For patients who died within 30 days of surgery, we are interested in the cause of death. The UCAUSE will only be used internally by HDNS to create flags for these causes of death as categorized according to ICD codes as follows: acute myocardial infarction (I21 to I22, I24), cardiac arrest (I46.0, 146.1, 146.9), ventricular tachycardia (I47.2), shock (R57, T81.1) excluding septic shock (R57.2), congestive heart failure (I50.0, I50.1, I50.9), pulmonary edema (J81), complete heart block (I44.2), pneumonia (J13 to J18, J69.0, J69.8, J95.4), pulmonary embolism (I26), acute respiratory failure (J95.1, J95.2),

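### The overnight-stay rule in Data linkage Step 2b removes nearly all in-hospital deaths on the surgery date, so intraoperative mortality is almost unobservable and the primary outcome is, without saying so, conditional on surviving that day

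*Combined protocol and SAP*

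**What the plan says.** **Eligibility.** Methodology, Data linkage, Step 2 (HDNS: CIHI DAD), item b reads "Exclude patients with Length of Stay (LOS) ≤ 1". For patients with several operations it adds that "the first surgery with a LOS >1 (i.e. at least overnight stay) will be included". Deaths are not exempted.

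**Definition of LOS.** The LOS row of Appendix 1 gives the formula as "discharge date minus PDATE + 1 (includes day of surgery" and makes it part of the inclusion criteria. It explains: "We have chosen to standardize LOS to only include duration of stay after surgery". Days in hospital before the operation therefore do not count.

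**Outcomes.** Specific aims, Hypothesis and II. Outcomes name 30-day all-cause postoperative mortality as primary. The Mortality row of Appendix 1 says it is "derived from DOD within 30 days from PDATE". The postoperative day of death is a "Derived discrete (n = 1, 2, 3... 30) variable", so it has no day 0. Intraoperative mortality is secondary outcome 5. Cohort characteristics plans to describe the timing of deaths as intraoperative or postoperative, and Appendix 1 requests OPDEATH, which flags death in the operating room.

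**The concern.** The rule is meant to screen out day surgery, but it is applied to a length of stay that death itself cuts short. A patient who dies on the surgery date cannot meet it, so eligibility depends partly on the outcome.

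Two things are at stake. First, an event listed as a secondary outcome nearly always makes the patient ineligible. The best model is to be applied to the secondary outcomes (Evaluating model performance), and here it would have almost no events. Second, a reader of the results would take the primary outcome as all-cause mortality from the procedure date, whereas the cohort delivers mortality after the surgery date. The overnight-stay restriction is stated openly in several places. Its effect on deaths is stated nowhere, including Limitations.

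**Working it through.** **The plan's own figure.** Power calculation: 24,000 × 0.017 = 408 deaths in the derivation set. At 10 events per predictor, 408 / 10 = 40.8, which the plan gives as 41. This reproduces.

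**Date arithmetic.** The formula is LOS = discharge date − PDATE + 1, from Appendix 1. The discharge date is taken as the date of an in-hospital death. The documents do not state this, but Appendix 1 records in-hospital death as a discharge disposition, which supports it. The exclusion test is LOS ≤ 1.

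| Case | LOS | Step 2b |
|---|---|---|
| Death on PDATE, admitted that day | 0 + 1 = 1 | excluded |
| Death on PDATE, admitted 3 days earlier | 0 + 1 = 1 | excluded |
| Death on the day after PDATE | 1 + 1 = 2 | kept |
| Death on the true surgery date, PDATE one day early | 1 + 1 = 2 | kept |
| Death on the true surgery date, PDATE one day late | −1 + 1 = 0 | excluded |

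Counted from admission, LOS in the second row would be 4 and the patient would stay in. The LOS row of Appendix 1 rules that reading out.

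**What can still reach outcome 5.** Three kinds of case remain: a PDATE recorded one day early (Step 2a tolerates a one-day mismatch), an operation that crosses midnight with death on the next date, and, if OPDEATH is recorded per admission, a death at a later reoperation. The documents give no count for any of them. Under the privacy rules only cell counts above 5 are reported, so the remainder may not be publishable.

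**Size of the loss.** The documents do not give the share of deaths that fall on the surgery date. I assume 1-10% and let the plan's 1.7% in-hospital rate stand in for 30-day mortality.

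- Derivation set, deaths lost: 408 × 0.01 = 4.1 to 408 × 0.10 = 40.8.
- Deaths left: 403.9 to 367.2, which support 40.4 to 36.7 predictors at 10 events each.
- Whole cohort: 35,000 × 0.017 = 595 deaths, of which 6.0 to 59.5 are lost.
- Mortality in the whole cohort: from 1.70% to (595 − 5.95) / (35,000 − 5.95) = 1.68%, or to (595 − 59.5) / (35,000 − 59.5) = 1.53%.

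**The case against.** The best defence is that an eligibility rule defines the population and does not contradict an outcome measured within it. The overnight-stay cohort is declared, the outcome is called postoperative, and day of death is numbered from 1. All of this fits an outcome that starts the day after surgery. This stands. A reader might infer that Step 2b contradicts the primary outcome, but the documents do not support that: a 30-day limit from PDATE is an upper bound and can be computed without day-0 events. What remains is that no section says the outcome is conditional on surviving the surgery date.

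It can also be said that a score calculated at the end of surgery (Background and significance) has no use for patients who die on the table. That is fair for operating-room deaths. It does not cover patients who leave the operating room and die later that day, whom closer monitoring is meant to help.

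The OPDEATH row of Appendix 1 mentions only descriptive use, which softens the point about outcome 5. II. Outcomes nevertheless lists it as a secondary outcome, and the descriptive breakdown would be just as empty.

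Step 2a makes the Innovian surgery date the gold standard. If that date, and not PDATE, governed LOS, the misdating exceptions would vanish, but surgery-date deaths would still be excluded.

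Two further inferences go beyond the documents. One is that the exclusion biases the hemodynamic associations in a known direction; nothing in the plan allows that to be derived. The other is that linkage is already complete. The artifact sub-study refers to an existing Innovian dataset, but the plan places artifact removal before linkage, so this does not show that the Step 2c list has been sent.

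**Conclusion.** The point holds. Taking discharge date as date of death, Step 2b and the LOS definition together exclude nearly every in-hospital death on the index surgery date. Secondary outcome 5 and the intraoperative breakdown cannot be delivered in any useful form. The primary outcome is sound as a quantity but mislabelled: it is 30-day all-cause mortality among overnight-stay patients who survive the day of surgery.

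The numerical effect on the primary analysis is modest. Even if 10% of deaths fall on the surgery date, about 367 derivation deaths remain. That share is an assumption. The mechanism needs no outside figure. This should be fixed because an outcome is unworkable and a label is wrong; it is not a sample-size problem.

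**What to change.** **Recommended.** Keep Step 2b and change the following.

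1. In Specific aims, Hypothesis, II. Outcomes and the Mortality row of Appendix 1, state the primary outcome as 30-day all-cause mortality among patients surviving the day of surgery. The existing numbering of day of death from 1 then fits.
2. Drop secondary outcome 5 and the intraoperative versus postoperative breakdown in Cohort characteristics.
3. Ask HDNS for the number of surgery-date deaths excluded by Step 2b, reported as 5 or fewer if small, and add a sentence to Limitations.

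The cost is wording plus one count. HDNS already holds the date of death for internal use.

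**Alternative, if the investigators want to keep outcome 5.** Exempt in-hospital deaths on the day of surgery from Step 2b, let such an operation qualify as the index surgery, number day of death from 0, align the overnight-stay wording, and repeat the primary analysis without these deaths. OPDEATH, discharge disposition and date of death are already in Appendix 1.

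This must be done before the list in Step 2c is sent ("HDNS provides Innovian-HSM the final list of included patients (patient ID and surgery date"), because Innovian-HSM data follow only for listed patients. Later, it would need a new extraction and linkage. The drawback is outcome-dependent entry: some intended day-surgery deaths would come in without comparable survivors, and Appendix 1 has no variable to flag them. Outcome 5 might also stay thin. To exceed the cell limit it needs 6 operating-room deaths, or 6 / 595 = 1.0% of all deaths in the whole cohort.
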